Human Subjects Protocol

VA Puget Sound IRB

Medication Optimization Using Pharmacogenetic Testing and the Genomind Drug Interaction Guide (G-DIG) to Reduce Polypharmacy in a Mental Health Population

MIRB#: 01600

Funding Agencies:
Investigator Initiated Grant – Genomind Incorporated
Seed Grant – VA Research & Development

[name]

Protocol Version 4; March 21, 2018

Abstract

1. Objective(s) and Hypotheses:

Use of polypharmacy has significantly increased over the past two decades, which has unproven clinical benefit and increased the risk of drug-drug interactions and adverse side effects. Pharmacogenetic assays have the purported benefit of being able to predict response(s) to specific medication based on genetic markers. One such assay is the Genecept® Assay produced by Genomind, which detects 63 allele polymorphisms of 18 genes. In addition, Genomind has developed the Genomind Drug Interaction Guide (G-DIG), which examines drug-drug-gene interactions. This computerized decision tool for medication providers uses the genetic information from the Genecept Assay to look at the current medications being utilized to determine if there are specific drug-drug interactions that may be relevant given the individual's specific genetic test results.

The study will test the following hypotheses:

- 1) Use of pharmacogenetic testing and the G-DIG will reduce psychiatric polypharmacy.
- 2) Use of pharmacogenetic testing and the G-DIG information provided to providers will result in changes to the medication treatment plan based on the new information.
- 3) Use of pharmacogenetic testing and the G-DIG will improve overall clinical symptoms as measured by the CGI (secondary analyses).
- 4) Pharmacogenetic testing and the G-DIG will reduce healthcare costs associated with medications (secondary analyses).
- 5) Pharmacogenetic testing will reduce clinical symptoms of anxiety and depression and improve quality of life (secondary analyses).

2. Research Design:

This is a 12-week open-label, naturalistic study of the provision of pharmacogenetic testing information to both providers and patients. Veterans who have been prescribed polypharmacy and are experiencing a sub-optimal effect will be eligible for the study. Medication providers who are participating in the study as sub-investigators will refer their own patients for the study. Participating subjects will sign informed consent and a sample will be obtained in order to complete the pharmacogenomic testing. Providers will utilize the pharmacogenetic assay results along with the G-DIG tool to design an optimized medication regime. The overall global level of symptoms and other patient symptoms measures will be administered at baseline, 6-weeks, and 12-weeks.

3. Methodology

Fifty Veterans within the VAPSHCS who are prescribed polypharmacy, as defined as five or more medications, with at least two prescribed for a mental health diagnosis, and have a sub-optimal treatment effect will be enrolled in this study. The provider's medication plans will be compared before and after the pharmacogenetic assay information is provided. Number of medications will be reviewed to determine any

reduction in polypharmacy and healthcare costs. The clinical global improvement scale (CGI) and patient assessments, including measures of depression, anxiety, PTSD, insomnia, pain, drug and alcohol use, quality of life, side effects, and medication adherence will be administered at baseline, 6-weeks, and 12-weeks.

List of Abbreviations

AE	Adverse Event
CRF	Case Report Form
DSMB	Data Safety Monitoring Board
G-DIG	Genomind Drug Interaction Guide
HIPAA	Health Insurance Portability & Accountability Act
IRB	Institutional Review Board
PHI	Protected Health Information
PI	Principal Investigator
PTSD	Post-Traumatic Stress Disorder
R&D	Research & Development
SAE	Serious Adverse Event
Sub-I	Sub Investigator
TBD	To Be Determined
VAPSHCS	VA Puget Sound Health Care System

Contents

Protocol Title:	6
1.0 Study Personnel	6
2.0 Introduction.....	6
3.0 Objectives.....	8
4.0 Resources and Personnel	9
5.0 Study Procedures.....	9
5.1 Study Design.....	9
5.2 Recruitment Methods.....	13
5.3 Informed Consent Procedures	14
5.4 Inclusion/Exclusion Criteria	14
5.5 Study Evaluations	15
5.6 Data Analysis	15
5.7 Withdrawal of Subjects.....	16
6.0 Reporting.....	16
7.0 Privacy and Confidentiality	17
8.0 Communication Plan	17
9.0 Information Security and Data Storage/Movement.....	17
10.0 References.....	18

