5.4 Inclusion/Exclusion Criteria

Inclusion Criteria

1. Currently receiving outpatient treatment for a mental health diagnosis within the VA Puget Sound Health Care System from a provider who is a sub-investigator on this study.
2. Currently experiencing a sub-optimal medication response as assessed by either continued symptoms or medication side effects, which in the opinion of their treating provider would indicate a change in medications would be warranted.
3. Currently prescribed polypharmacy, as defined as five or more medications, with at least two being for a mental health diagnosis. Also allowable would be one medication for a mental health diagnosis and another medication for side effects related to a medication prescribed for the mental health diagnosis.
4. Between the ages of 18 and 75.

Exclusion Criteria

1. Any mental or physical health diagnosis, which in the opinion of their treating prescriber would prevent them from being compliant on a medication regimen or being able to complete the study measures.
2. Current/active diagnosis of severe alcohol or drug use disorder.
3. Serious medical or mental health symptoms requiring immediate stabilization and/or hospitalization.
4. Impaired decision making capacity that in the clinical judgement of their provider would affect their ability to provide informed consent.
5. Self-identification as being currently pregnant.

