5.5 Study Evaluations

Measures:

The primary measure to determine clinical effectiveness is the Clinical Global Improvement Scale. This scale will be completed both by the provider and the study coordinator (or study personnel collecting the assessment measures).

The number of medications and treatment utilization will be collected by chart review of the subject's medical record at baseline and at 12 weeks to determine any change in the number and type of medications prescribed.

Any differences between the initial medication plan developed by the provider prior to receiving the pharmacogenetic assay results, the medication optimization plan developed by the provider after the use of the G-DIG tool, and actual clinical practice will be noted. The number and cost of medication changes will also be evaluated.

Participant assessments administered at baseline, 6 and 12 weeks will include measures from the Behavioral Health Lab (BHL; Oslin et al., 2006). These measures will include a demographic questionnaire, GAD-7 (Anxiety), PHQ-9 (Depression), PCL-5 (PTSD), Insomnia Severity Index, Chronic Pain, Screening for Alcohol and Drug use, RAND Health Survey, and Side Effects and Adherence (See Appendix A). The results of the BHL assessments will be placed into the subject's medical record. Participants will also be asked about smoking.

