5.6 Data Analysis

Analysis Plan and Power Calculations: The primary and secondary hypotheses will be calculated using within group t-tests using the Statistical Package for the Social Sciences (SPSS). A statistical power analysis was performed for sample size estimation. The effect size was estimated to be medium (0.50) using Cohen's (1988) criteria. With an alpha = .05 and power = 0.80, the projected sample size needed with this effect size is approximately N = 34 to conduct a single sample t-test. Thus, our proposed sample size of N = 50 should be more than adequate to analyze the main hypothesis for this study and should also allow for expected attrition and the analysis of our secondary hypotheses.

Interpretation: Interpretation of these hypotheses should demonstrate whether the Genecept® Assay and the G-DIG tool are beneficial to Veteran prescribed polypharmacy in order to reduce polypharmacy and improve clinical symptoms. The primary limitation to this study is that there is no control group, so attribution of any change to the pharmacogenetic assay should be done with reservations. If this study shows promising results, future studies should include a randomized control group. Another limitation is sample size. Though with our estimated effect size, we should have power to detect significance, larger sample sizes are preferred to increase generalizability to a larger population.

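### Entry sets a floor on the medication count and hypothesis 1 tests the change in a chart count against zero, so regression to the mean favours a fall, by an amount the plan does not allow anyone to judge

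*Combined protocol and SAP*

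**What the plan says.** The abstract (3. Methodology) describes the patients as Veterans "who are prescribed polypharmacy, as defined as five or more medications, with at least two prescribed for a mental health diagnosis". Section 5.4 sets the entry floor: "Currently prescribed polypharmacy, as defined as five or more medications, with at least two being for a mental health diagnosis". It also admits a patient with one mental health drug plus one drug for its side effects. Neither 5.2 nor 5.4 requires a minimum time on the regimen or a second qualifying count, and the study map in 5.1 shows no repeat count during the 2-week baseline period.

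Section 5.5 takes the outcome from the "subject's medical record at baseline and at 12 weeks to determine any change in the number and type of medications prescribed". Section 5.6 gives the test: "The primary and secondary hypotheses will be calculated using within group t-tests", which means mean change against zero. Hypothesis 1 (section 3.0) speaks of psychiatric polypharmacy. No section says whether its endpoint is the total count or the psychiatric count.

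Section 5.6 names the lack of a comparator as the main limitation and advises caution in attributing change to the assay. It mentions neither regression to the mean nor selection on the outcome.

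**The concern.** A floor on a fluctuating quantity selects patients partly for being above their own usual level on that day. When they are counted again, they tend to drift back. The value expected without an assay effect is then below zero, while the test uses zero.

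This happens with long-term drugs as well as short courses, and whether the endpoint is the total or the psychiatric count, because entry sets a floor on both. The bias points towards the result the trial hopes to show on its first-listed hypothesis. Medication cost (hypothesis 4) is pulled the same way to the extent that it follows the count.

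**Working it through.** **The plan's own figure.** Inputs from 5.6: "The effect size was estimated to be medium (0.50) using Cohen's (1988) criteria" and "With an alpha = .05 and power = 0.80". A two-sided one-sample t-test (noncentral t) gives n = 33.4, so 34, which matches "the projected sample size needed with this effect size is approximately N = 34 to conduct a single sample t-test". A one-sided test would give 27, so the plan is evidently two-sided and the nominal chance of a false *fall* is 2.5%. With N = 50 the power at d = 0.50 is 0.93, and an observed mean fall of 2.01/√50 = 0.28 SD is already significant. The sample size is not in error.

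**Model (assumed, not in the documents).** Each patient has a usual count λ. The baseline count X is Poisson(λ). Over 12 weeks each drug stops with probability q and new drugs start at rate qλ, so the unselected mean is constant and there is no assay effect. Then:

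- expected change given X = q(λ − X)
- expected change among those enrolled = q × (mean λ of those enrolled − mean X of those enrolled), which is negative once there is a floor on X.

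**Check by hand: psychiatric count, floor of 2, λ = 2 for everyone, q = 0.2.**

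- P(X ≥ 2) = 1 − e⁻²(1 + 2) = 0.594
- Mean X given X ≥ 2 = (2 − 2e⁻²)/0.594 = 1.729/0.594 = 2.91
- Expected change = 0.2 × (2 − 2.91) = −0.18 drugs
- Simulated SD of change 0.96, so SE = 0.96/√50 = 0.136, and the shift is 0.183/0.136 = 1.35 SE
- Approximate chance of a significant fall = Φ(1.35 − 2.01) = Φ(−0.66) ≈ 0.25; simulation gives 0.265.

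**The same check at the harmless end: total count, floor of 5, λ = 12, q = 0.2.** Nearly everyone qualifies, mean X is 12.06, and the expected change is 0.2 × (12 − 12.06) = −0.012 drugs. Simulation gives a significant fall in 2.8%.

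**Simulated chance of a significant fall with no assay effect, N = 50.**

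| Count and floor | Usual mean | q 10–30%, between-patient SD half the mean | q 5–30%, SD from zero to half the mean |
|---|---|---|---|
| Total, ≥5 | 4 | not run | 10–77% |
| Total, ≥5 | 5 to 8 | about 5–23% | 6–24% at 6; 4–8% at 8 |
| Total, ≥5 | 10 to 12 | about 3–5% | 3–5% |
| Psychiatric, ≥2 | 1 | not run | 15–88% |
| Psychiatric, ≥2 | 1.5 to 2 | 12–46% | 7–38% at 2 |
| Psychiatric, ≥2 | 3 to 4 | 5–12% | 5–14% at 3; 4–8% at 4 |

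The ranges are good to about one percentage point. For total means of 5 to 8 (first numeric column) the spurious mean fall is 0.06 to 0.35 drugs. The psychiatric rows apply the floor of two alone; they leave out the total floor of five and the side-effect-drug exception, which softens the floor of two.

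**The symmetric contrast (week +12 minus week −12).** Under this model both counts have the same distribution given X, so the expected difference is zero and a false fall occurs in 2.3 to 2.7%. That follows from the model's construction and does not validate the contrast for this trial. Its SD is 1.32 to 1.39 times larger. A true d of 0.50 becomes 0.50/1.32 = 0.38 to 0.50/1.39 = 0.36, with power 0.75 to 0.70 at N = 50 and 0.65 to 0.60 with 40 completers. If counts had risen by 0.25 SD in the 12 weeks before consent, the effective size is (0.50 − 0.25)/1.35 = 0.185 and power is about 0.25.

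**The case against.** The strongest reply has four parts.

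1. *The size rests on assumptions.* This stands. The documents give no count distribution, SD of change or turnover rate. At usual totals of 10 or more the distortion is close to nothing, and nothing in the plan says that usual psychiatric counts lie near two.

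2. *Counts need not be stable.* This also stands. Section 5.4 requires the provider to judge already that a medication change is warranted. That may add or remove drugs whatever the assay shows, so a net fall without an assay effect is not certain. It is, though, one more reason why zero need not be the no-effect value.

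3. *The test is valid for what it tests.* Strictly, a paired t-test asks whether mean change in the enrolled group is zero. If that mean truly drifts down, rejection is not a type I error of that test. A reader might infer that the t-test is invalid or that alpha is breached. The accurate statement is that rejection cannot be read as an assay effect at the nominal rate.

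4. *It is already disclosed.* Only in part. The caution in 5.6 is about attribution in general. It does not name this one-directional mechanism or correct the estimate, and the same section still expects the results to show whether the tools are beneficial.

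**Conclusion.** The concern holds as a bias towards a fall of unknown size, conditional on counts fluctuating around a stable level. Under the stated assumptions the chance of a significant fall without an assay effect runs from close to the nominal 2.5%, when usual counts lie well above the floor, to several times that when they lie near it. The plan collects nothing that shows where this trial sits.

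Three stronger readings are not supported:

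- *Drug turnover will produce a fall, so any fall seen is an artefact.* The documents establish neither the turnover nor the stability that this needs.
- *The entry count and the endpoint are the same count.* The floor of five covers all medications, hypothesis 1 concerns psychiatric polypharmacy, and the endpoint count is not defined. The mechanism applies to either count, but its size differs.
- *A claim should depend on the symmetric contrast.* That contrast is unbiased only if counts are symmetric around consent, which is doubtful for patients enrolled with a sub-optimal response. Its power also falls below the plan's 0.80.

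**What to change.** - **5.5:** have the existing chart review also extract the active medication list dated 12 weeks before consent.
- **5.6:** state which count hypothesis 1 uses. Pre-specify week +12 minus week −12 as a sensitivity analysis for hypothesis 1, and for medication cost in hypothesis 4. Report it beside the baseline-to-week-12 change, and not as a condition for a claim.
- **5.6:** report the contrast between the provider's plan written before the results and the plan written after the assay. Section 5.5 already collects both. They concern the same patient at nearly the same time, so selection on the baseline count does not bias the contrast. It measures intended changes and not the week-12 regimen, so it complements the chart count.
- **5.6, limitations:** name regression to the mean from the entry cut-off.

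The cost is one more dated list per patient from a record already under review, plus a few sentences, with no extra patient contact and no change to eligibility. The downsides should be stated with the analysis: power of about 0.70 to 0.75 at d = 0.50 with N = 50, a conservative result if counts were rising before entry, and loss of patients who have no earlier VA record.

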2.0 Introduction

Prevalence of Polypharmacy: Use of polypharmacy has significantly increased over the past two decades. The National Ambulatory Medical Care Survey from 1996-2006 found the number of psychotropic medications has significantly increased, with a 40.1% increase in the median number of medications prescribed (Mojtabai et al., 2010). This increase is even more significant for people over the age of 65, with the same survey finding that between 2004 and 2013, polypharmacy in older adults increased 145% (from 1.50 million to 3.68 million). In developed countries, approximately 30% of individuals 65 and older are prescribed five or more medications (Qato et al., 2008).

Polypharmacy is becoming more common in mental health populations. Individuals with bipolar disorder are at increased risk with approximately 1 in 5 individuals with bipolar prescribed at least four medications (Goldberg et al., 2009). Persons with schizophrenia have been shown to be prescribed antipsychotic polypharmacy in up to 50% of cases in some settings (Barnes & Paton, 2011). Veterans with PTSD and traumatic brain injury have also been shown to be at increased risk for polypharmacy (Collett et al., 2016).

Risks Associated with Inappropriate Polypharmacy: These increases in polypharmacy increase the risk of drug-drug interactions, adverse side effects,

with unproven clinical benefit. Higher levels of antipsychotic daily doses have been associated with decrements in information processing speed and verbal memory. (Rehse et al., 2016). Higher doses of antipsychotics may in turn lead to additional adverse effects, some of which are commonly treated with anticholinergics, leading to additional adverse effects (Barnes & Paton, 2011; Minzenberg et al., 2004). Reducing polypharmacy has been shown to have clinical improvements. In a population of individuals with schizophrenia, reducing antipsychotic polypharmacy led to improvements in cognition along with reductions in symptoms (Kawai et al., 2006).

Older adults may be at particular risk for the dangers of polypharmacy. Physiological changes that occur with age alter the pharmacokinetic and pharmacodynamics responses to medications, with resulting increased risks for polypharmacy as one ages. These adverse drug events can result in poor health, disability, cognitive impairment, hospitalization, increased risk of falls, and even death (Rehse et al., 2016; Zia et al., 2015). The number of prescribed medications is the single greatest predictor of inappropriate polypharmacy (Scott et al., 2015).

Veterans with PTSD and depression with traumatic brain injury may also be a risk for polypharmacy. Veterans prescribed polypharmacy have been shown to be at increased risk for suicide related behaviors, demonstrating that this is a vulnerable population, which may particularly benefit from medication optimization (Collett et al., 2016).

Barriers to Reducing Polypharmacy: Given the risks associated with polypharmacy, one might assume that there would be considerable pressure to reduce the number of medications, however, prescribers are often reluctant to remove medications for fear of destabilizing the patient. In order to reduce polypharmacy and the risks associated with it, several researchers have proposed methods by which the current medication regimen is examined and inappropriate medications removed (Lavan et al., 2016). These methods, however, are based on medication criteria, logical assumptions, and trial and error to gain the optimal medication regimen for each individual patient.

Optimizing Treatment Utilizing Pharmacogenetic Testing: The use of pharmacogenetics in clinical practice is a burgeoning field, but one that needs more research in order to determine the clinical and cost effectiveness of the receiving the pharmacogenetic test results. Pharmacogenetic assays have the purported benefit of being able to predict response(s) to specific medication based on genetic markers, thus, being able to identify medications that cannot be effectively processed and should be avoided, along with medications that may produce more optimal results.

One such assay in current use is the Genecept® Assay (Genomind, King of Prussia, Pennsylvania). The Assay detects 60 allele polymorphisms of 18 genes,

of which 12 code for pharmacodynamic proteins, e.g., receptors, transporters, enzymes, and ion channels. The remaining 6 genes code for pharmacokinetic variants, i.e., CYP450 alleles. Using a proprietary algorithm based on clinical data, the Assay suggests treatment options which might be more or less appropriate for the specific combination of genotype and indication. A naturalistic study of the use of this assay found that 87% of patients demonstrated clinical improvement as measured by the Clinical Global Impression Scale (CGI). Patients also showed decreases in depression, anxiety, and medical side effects, along with increases in their quality of life (Brennan et al., 2014). A recent systematic review of pharmacogenetic testing for the treatment of depression found that overall there was clinical benefit associated with the pharmacogenetic testing, but results for cost effectiveness were mixed (Rosenblat et al., 2017).

In addition to the Genecept® Assay, Genomind has developed the Genomind Drug Interaction Guide (G-DIG), which examines drug-drug-gene interactions. This computerized decision tool for medication providers, uses the genetic information from the Genecept® Assay to look at the current medications being utilized to determine if there are specific drug-drug interactions that may be relevant given the individuals specific genetic test results. This tool allows providers to not only identify medications that are not recommended based on their individual genetics, but also drug-drug interactions that may become problematic. Thus, this tool provides valuable information to providers in order to develop an optimized medication plan.

In summary, polypharmacy is associated with risks of drug-drug interactions, adverse side effects, with unproven clinical benefit. Pharmacogenetic testing may be able to predict an individual's response to medications based on their individual genetic results, which may be beneficial in reducing polypharmacy by eliminating medications that are not beneficial, leading to medication optimization. These pharmacogenetic assays are new to the market and have limited research data. The use of this assay to reduce polypharmacy has never been tested.

